18 PROTOCOL VERSION ≥3.2: MAINTENANCE PHASE

Appendix 16 Maintenance Phase

1. INVESTIGATIONAL PLAN FOR THE MAINTENANCE PHASE

1.1. Maintenance Phase Design

As of Version 3.2 of the protocol, Karyopharm will terminate the Primary Treatment Phase of the study and the remaining patients on study will transfer to the Maintenance Phase of the study to continue treatment with selinexor and/or survival follow-up. These patients will be followed primarily for safety. The patients will be allowed to receive treatment until disease progression, Investigator or patient decision to discontinue study treatment, pregnancy, unacceptable AEs or toxicity that cannot be managed by supportive care, withdrawal of consent, death, or termination of the study. Data from the Maintenance Phase will be collected in a separate database to allow locking of the Primary Treatment Phase database after initiation of the Maintenance Phase.

1.1.1. Transition from Primary Treatment Phase to Maintenance Phase

Patients will complete their current cycle in the Primary Treatment Phase and then transition to the Maintenance Phase of the study (Maintenance Phase Cycle 1 Day 1).

1.1.2. Study Treatment

The treatment under investigation in the Maintenance Phase of the study (i.e., the “investigational medicinal product” [IMP]) is selinexor 20 mg tablets for oral administration. Patients will continue on the same dose of selinexor (as they were receiving prior to this amendment) and dosing may be modified as needed according to the guidelines in this protocol. For more details on selinexor dosing see Section 1.1.2.2.

1.1.2.1. Selinexor Tablets

Selinexor 20 mg tablets will be provided as coated, immediate-release tablets for oral administration in blister packs. Patients will be given a supply of tablets for non-clinic dosing days. Additional information about selinexor is available in the *Selinexor IB*.

1.1.2.1.1. Labeling

All labels will include conditions for storage, lot number, and other pertinent information such as Sponsor and caution statement. Selinexor should not be used after the expiration date.

1.1.2.1.2. Dispensing Directions

Dispensing instructions for selinexor will be provided in the *Pharmacy Manual*.

1.1.2.1.3. Storage

Selinexor tablets should be stored at or below 86°F (30°C) in a secured area with access restricted to the site staff pharmacist or designee(s) at room or refrigerated temperature.

Room temperature storage is preferred. The tablets must not be stored at freezer temperatures or frozen. Refer to the *Pharmacy Manual* for detailed information on selinexor storage, stability, and administration.

1.1.2.1.4. Accountability

The Investigator or designee must maintain an accurate record of the shipment and dispensing of study treatment in a drug accountability log. Study treatment accountability will be noted by the clinical research associate during site visits and at the completion of the study. Patients will be asked to return all unused study treatment and packaging on a regular basis, at the time of study treatment discontinuation or at the end of the study (See Section 1.1.5 for definition of end of study).

1.1.2.2. Selinexor Dosing

Patients will receive the same selinexor dose and schedule during the Maintenance Phase as they received during the Primary Treatment Phase. Selinexor doses will be administered in 20 mg dose increments (e.g., 20 mg, 40 mg, 60 mg, etc.), consistent with the dose that the patient received in the Primary Treatment Phase of the study. However, if the patient was previously receiving a dose that was in between these 20 mg doses (e.g., 30 mg), the Investigator should consult with the Medical Monitor to determine the appropriate dose for that patient in the extension study. In no instance will the dose of selinexor exceed 70 mg/m².

1.1.2.3. Concurrent Treatments

Concurrent treatments, if any, that the patient received in the Primary Treatment Phase of the study, may be continued, at the discretion of the Investigator, but they will not be provided by Karyopharm. No new, additional treatments for the patient's malignancy (except for supportive care) may be added without the consent of the Medical Monitor.

The patient should receive concomitant treatment, as needed per standard of care and institutional standards. In addition, the patient will receive concomitant medications to treat symptoms, AEs, and intercurrent illnesses that are medically necessary as part of standard care. See Section 6.4.2 for prohibited medications.

1.1.3. Study Visits

During the Maintenance Phase of the study, assessments will take place at once-monthly visits for Cycles 1-7, then, provided that the patient is clinically stable, at every-other month visits thereafter for Cycles > 7. Each cycle will last 28 days.

1.1.4. Study Assessments

Safety will be assessed by adverse events (AEs) graded according to National Cancer Institute (NCI) Common Terminology Criteria for Adverse Events (CTCAE), v. 4.03 (as was done in antecedent studies). Disease assessment (response to treatment), where appropriate, to monitor disease status and response to therapy are not required per protocol, but it is requested that if possible the Investigator provide any disease status and response to treatment information obtained from disease assessments performed as part of institutional standard of care. Treatment will continue until disease progression,

Investigator or patient decision to discontinue study treatment, pregnancy, or unacceptable AEs or toxicity that cannot be managed by supportive care, withdrawal of consent, death, or termination of the study. See [Table 11](#) for a full schedule of assessments.

1.1.5. End of Treatment (EOT) and End of Study

The EOT Visit will occur ≤ 14 days after the patient receives their last dose of study treatment. A Safety Follow-up Call/Visit will be performed 30 days (+7 days) after last dose of study treatment. Follow-up ends when the patient has either completed that 30-day follow-up, withdrawn consent, been withdrawn by the Investigator, died, or been lost to follow-up. The end of study (EOS) will occur upon completion of the 30-day follow-up period for the last patient treated, or when Karyopharm has decided to end the study.

Table 11: Schedule of Assessments

Activity/Assessment ¹	Maintenance Phase				
	Cycle 1	Cycles 2-7 Visits	Cycles >7 (Every Other Cycle) Visits	End-of-Treatment (EoT) Visit	Safety Follow-up Call/Visit ⁵
	Day 1	Day 1 (± 3 Days)	Day 1 (± 3 Days)	≤ 14 Days Post Last Dose	30 Days (+ 7 Days) Post Last Dose
Clinical Assessments					
Weight and BSA	X	X	X	X	
Vital signs (BP, pulse, temperature)	X	X	X	X	
Complete physical exam	X				
Symptom-directed physical exam		X	X		
Ophthalmic examination	As clinically indicated				
Laboratory Assessments					
Urinalysis	X	X	X	X	
CBC with differential	X	X	X	X	
Complete serum chemistry	X	X	X	X	
Serum amylase and lipase levels ²	X	X	X	X	

	Maintenance Phase				
Activity/Assessment¹	Cycle 1	Cycles 2-7 Visits	Cycles >7 (Every Other Cycle) Visits	End-of-Treatment (EoT) Visit	Safety Follow-up Call/Visit⁵
	Day 1	Day 1 (± 3 Days)	Day 1 (± 3 Days)	≤ 14 Days Post Last Dose	30 Days (+ 7 Days) Post Last Dose
Coagulation tests	X	X		X	
Serum hCG pregnancy test ³	As clinically indicated				
Administration of selinexor in clinic ⁴	X	X	X		
AE/SAE reporting	THROUGHOUT				
Concomitant medication use	THROUGHOUT				
Telephone contact					X
Antineoplastic therapy after EoT				X	X
Abbreviations: AE: adverse event; BSA = body surface area; CBC = complete blood count; hCG = serum human chorionic gonadotropin; SAE = serious adverse event.					

¹ If study treatment is administered on a visit day, assessments for that visit should be performed before study treatment is administered. Disease assessments to monitor disease status and response to therapy are not required per protocol, but it is requested that if possible the Investigator provide any disease status and response to treatment information obtained from disease assessments performed as part of institutional standard of care.

² If not included in the complete serum chemistry panel, amylase and lipase levels must be performed at the same time points as the complete serum chemistry.

³ Applicable for women of childbearing potential only.

⁴ Dosing on days of clinic visits will occur in the clinic; dosing on subsequent days within a cycle will be done at home.

⁵ At the 30-day safety follow-up the patient should be contacted (by phone or visit) to assess survival status, disease status, overall medical condition, and collect information on any antineoplastic therapies used after discontinuation of study treatment.

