Safety assessments	
All serious adverse events (SAEs) and adverse events (AEs) for the Primary Treatment Phase and Maintenance Phase occurring from the signing of the ICF and from the start of treatment (i.e., Cycle 1 Day 1), respectively, and for up to 30 days after the last dose of study medication will be captured, documented, and reported, and graded according to CTCAE v.4.03.
 
Safety blood samples include complete blood count, clinical chemistry, including liver function test, and coagulation.

Statistical considerations	
Pre-planned subgroup analyses:
 
Part 1 of the study will enroll three cohorts of ovarian (Cohort A), endometrial (Cohort B), and cervical (Cohort C) cancers which will be evaluated independently. Part 2 of the study will enroll additional ovarian patients to evaluate efficacy and safety of once-weekly versus twice-weekly dosing.
 
Subtypes of each tumor (e.g., adenocarcinoma versus squamous

	
carcinoma) will be evaluated both together and separately. All enrolled patients are eligible for the analyses of toxicity and compliance. The treated population (modified intention-to-treat [mITT]) will consist of all patients who receive at least one dose of study medication and have at least one post-baseline efficacy follow-up assessment, unless the patient discontinued treatment prior to the first assessment due to death, toxicity, or PD. This population will be used for primary analyses of efficacy.

Sample size calculation	CCI 

INFORMATION TO BE PROVIDED REGARDING SAES/PREGNANCY

In the case of a serious adverse event (SAE) or pregnancy, contact Karyopharm by fax or email within 24 hours of knowledge.

Pharmacovigilance Department
Karyopharm Therapeutics Inc.
Email: [contact]
[contact] (US)
[contact] (Germany)

TABLE 1: SCHEDULE OF ASSESSMENTS FOR THE PRIMARY TREATMENT PHASE. See Section 18 (Appendix 16) for the Schedule of Assessments for the Maintenance Phase for the patients who continue treatment with selinexor and/or survival follow-up under version ≥3.2 of the protocol.

Assessment	Baseline (Within 14 days prior to C1 D1)	Day 1 of Each Cycle (-3 days)	Day 15 of Each Cycle (± 3 days)	After 6 Weeks of Treatment (± 7 days)	After 12 Weeks of Treatment Every 8 weeks (± 7 days) Until PD	End of Treatment (30 days ± 7 days post-last dose)	Survival Status (Every 3 months)
Informed consent ¹	X						
Inclusion and exclusion criteria	X						
Demographics	X						
Medical history ²	X						

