As of July 2016, 3 patients remain on treatment in the study, with additional patients in long-term survival follow-up. As of Version 3.2 of the protocol, Karyopharm will terminate the Primary Treatment Phase of the study and the existing patients will transfer to the Maintenance Phase of the study to continue treatment with selinexor and/or survival follow-up. These patients will be assessed primarily for safety. See Section 18 (Appendix 16) for objectives and treatment plan (including study treatment, schedule of assessments, dose modifications, and supportive care) for the Maintenance Phase of the study. The database for the Primary Treatment Phase will be reviewed and locked for analysis and the subjects in the Maintenance Phase will have their data entered into a separate database designed to collect data for extended treatment.

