## 4. STUDY ANALYSES

### 4.1. Patient Disposition

[figure not shown]
Patient disposition will be tabulated and presented separately by cohort and overall for Part 1 and by schedule and overall for Part 2. It will include the number enrolled, the number in each patient population for analysis, the number who discontinued treatment and the primary reason for discontinuation, the number who completed or withdrew from the study and primary reason for study withdrawal.

The EOT Visit will occur  $\leq 14$  days after the patient receives their last dose of study treatment. A Safety Follow-up Call/Visit will be performed 30 days (+7 days) after last dose of study treatment. Follow-up ends when the patient has either completed that 30-day follow-up, withdrawn consent, been withdrawn by the Investigator, died, or been lost to follow-up. The end of study (EOS) will occur upon completion of the 30-day follow-up period for the last patient treated, or when Karyopharm has decided to end the study. Reason for treatment and study discontinuation will be recorded on the eCRF.

A by-patient data listing of study completion information including the reason for study withdrawal, if available, will be presented. By-patient listings of inclusion/exclusion criteria not met and follow-up visit survival status will also be presented.

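### Appendix 16 takes over patients for survival follow-up but schedules no survival contact beyond 30 (+7) days after last dose, so 24-month OS in Part 2 may not be estimable

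*Protocol*

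**What the plan says.** **Transfer.** Appendix 16, 1.1, provides that "the remaining patients on study will transfer to the Maintenance Phase of the study to continue treatment with selinexor and/or survival follow-up". Protocol 1.4 shows that both kinds of patient existed: "As of July 2016, 3 patients remain on treatment in the study, with additional patients in long-term survival follow-up". The Table 1 caption refers these patients to the "Schedule of Assessments for the Maintenance Phase for the patients who continue treatment with selinexor and/or survival follow-up" in Appendix 16, and Protocol 3.1 and 5.2 point to the same place.

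**Maintenance Phase follow-up.** Appendix 16, 1.1.4, refers to Table 11 "for a full schedule of assessments". Table 11 has no survival column. Its only survival check is in footnote 5: "At the 30-day safety follow-up the patient should be contacted (by phone or visit) to assess survival status". Section 1.1.5 then closes follow-up: "Follow-up ends when the patient has either completed that 30-day follow-up, withdrawn consent, been withdrawn by the Investigator, died". It also closes the study: "The end of study (EOS) will occur upon completion of the 30-day follow-up period for the last patient treated", or earlier if the sponsor so decides.

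**Follow-up elsewhere.** Protocol 3.1, 3.2.3 and 5.3.4, and Protocol Table 1, require a survival call about every 3 months once treatment stops. Protocol 5.5 keeps discontinued patients under follow-up for progression and survival. SAP 1.2.1, 1.2.3.1 and Table 1-1 say the same.

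**SAP 4.1.** This section opens with "Patient disposition will be tabulated and presented separately by cohort and overall for Part 1 and by schedule and overall for Part 2". It then repeats the Appendix 16 sentences on the end of follow-up and the end of study, with no limit to the Maintenance Phase.

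**Endpoint.** OS with 12- and 24-month rates is a secondary objective (Protocol 2.1.2). SAP 4.3.2 item 4 takes both rates from the Kaplan-Meier curve for each cohort.

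**The concern.** A patient who is more than 37 days past the last dose at transfer is sent to a schedule that contains no contact for her. A patient still on drug has one survival check after stopping and then none. A site that follows Appendix 16 literally would stop the calls; a site that follows Protocol 3.2.3 and 5.5 would continue them. Both would be complying with current text.

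The stake is how mature the survival data are. Part 2 was added by a later amendment, so its patients are the ones least likely to have reached month 24 when the Maintenance Phase was created. If contact stops then, deaths before month 24 go unseen and the curve may end before the time point at which it is to be read.

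**Working it through.** The plan gives no figure to reproduce here, because the sample-size sections are redacted. The check compares the follow-up rules and then uses the document dates.

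**1. Rules side by side**

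| Source | Survival contact after treatment stops | End of study |
|---|---|---|
| Protocol synopsis | about every 3 months | 30 days after the last progression |
| Protocol 3.2.3, 3.3, 5.3.4, 5.5 | about every 3 months; still followed for survival | 30 days after the last progression, unacceptable toxicity, consent withdrawal or death |
| Appendix 16, 1.1.5 and Table 11 | once, at 30 (+7) days | 30-day follow-up of the last patient treated, or sponsor decision |
| SAP 1.2.1, 1.2.3.1, Table 1-1 | about every 3 months; still followed for survival | not stated there |
| SAP 4.1 | ends with the 30-day follow-up | as Appendix 16 |

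There are three distinct end-of-study wordings, since SAP 4.1 repeats Appendix 16. None depends on completing survival follow-up.

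**2. Longest possible Part 2 follow-up at Version 3.2**

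Inputs: Version 2.0, which added the 32 Part 2 patients, is dated 9 September 2014; Version 3.2 is dated 4 August 2016 (change summaries). One month is 30.4375 days.

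- 9 September 2014 to 4 August 2016 = 695 days; 695 / 30.4375 = 22.8 months.
- Adding one 28-day cycle before transfer (Appendix 16, 1.1.1): 723 / 30.4375 = 23.75 months.

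Both are below 24 months. On these dates, every living Part 2 patient needs contact after transfer to contribute to OS24. Appendix 16 still sees regularly only those on drug, 3 across the whole study in July 2016.

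**3. Part 1**

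The start is given as January 2014. From 1 January 2014 to 4 August 2016 is 946 days; 946 / 30.4375 = 31.1 months. Early Part 1 patients could already have passed month 24.

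**4. Later adoption**

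Protocol 11 requires approval before a change takes effect. With adoption 3 months later (4 November 2016), patients first dosed within 56 days of Version 2.0 have reached month 24. With adoption 6 months later (4 February 2017), the window is 148 days.

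**5. Patients who should be at risk at month 24 if the calls continue**

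Per 16-patient schedule, with exponential survival and assumed median M, the expected number is 16 × 0.5^(24/M):

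- M = 9 months: 2.5
- M = 12 months: 4.0
- M = 16 months: 5.7

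**6. Illustration only**

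Accrual and adoption dates are not in the documents. Assumptions: uniform accrual over 6 to 16 months from Version 2.0, median time on drug 3 or 4 months, median survival after stopping 6 or 12 months, 5% of patients dying on treatment, and only runs with at most 3 Part 2 patients on drug at the cut-off. One 16-patient schedule is analysed with Appendix 16 applied literally. The curve counts as reaching month 24 if someone is followed that far or it has already fallen to zero.

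| Adoption lag | Curve reaches month 24 | Deaths before month 24 unseen |
|---|---|---|
| none | 13–38% of runs | 1.1–3.7 |
| 3 months | 51–88% | 0.3–2.4 |
| 6 months | 70–100% | 0–1.4 |

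With no lag, OS12 moves by 0 to 1 point. Compared with a plain calendar cut-off for everyone, stopping contact soon after the last dose adds 0 to 1.5 points to OS24. In Part 1 (21 per cohort, assumed accrual 8 to 16 months) the curve reaches month 24 in 83–100% of runs.

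**The case against.** **Safety reading.** In Appendix 16, 1.1.5, the 30-day follow-up refers back to the safety call in the sentence before it. The Version 3.2 change summary does not list 3.2.3 or 5.5 among the modified sections. On that reading the 3-monthly calls continue and nothing is lost. This is a fair reading and it stands as a possibility. But 1.1.5 says follow-up ends without limiting it to safety, and the cross-references name survival follow-up.

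**Sponsor's choice.** OS is an objective of the Primary Treatment Phase. The Maintenance Phase is for continued access and safety, its endpoints omit OS, and the primary database is to be locked. A cut-off for OS at lock would be legitimate, but the plan does not declare one. It keeps OS24, transfers patients expressly for survival follow-up, and in Protocol 16 makes the final report wait for long-term follow-up.

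**SAP 4.1 is about disposition.** It does not instruct sites, it also lists follow-up survival status, and OS censoring is set in 4.3.2. That is correct, so the sentence does not itself change the OS estimate. It still contradicts Table 1-1. Protocol 8.5 is no help to either side: it permits a later survival summary without requiring one.

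**OS in Part 2 is unclear.** SAP 3.4 gives the OS baseline for Part 1 only, whereas SAP 1.2.5.1 analyses both parts for all secondary endpoints. This stands and needs reconciling.

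**Low stakes.** The primary endpoint is untouched, SAP 3.7 calls secondary evidence preliminary, and OS24 from 16 patients is imprecise in any case. All true; this limits the weight of the point but does not remove it.

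A reader might also infer that no text says which rule governs a transferred patient. That goes too far: the cross-references lead to Appendix 16. What is missing is any statement on whether the 3-monthly calls continue.

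**Conclusion.** The contradiction is real and should be corrected. Transferred patients are directed to a schedule with no survival contact after 30 (+7) days and nothing for those already off drug, and SAP 4.1 carries the same end into the Part 1 and Part 2 analysis.

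The firm part of the size is the date bound. At most 22.8 months separate the opening of Part 2 from Version 3.2, so if Appendix 16 is applied literally at that date, no Part 2 patient has 24 months of follow-up and OS24 there may not be estimable. This depends on the reading of 1.1.5, on the adoption date, and on OS24 being intended for Part 2. The simulated ranges only illustrate the direction and the strong effect of the adoption lag.

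Two stronger inferences are not supported. The documents do not show that survival follow-up was in fact stopped or that OS24 in Part 2 is lost. Nor do they show material bias from treatment-linked censoring: under the stated assumptions it adds at most about 1.5 points beyond an ordinary calendar cut-off. OS12 and Part 1 are little affected.

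**What to change.** - **Appendix 16, 1.1.5 and Table 11:** add the existing 3-monthly survival call for all transferred patients, on or off drug, until death, withdrawal, loss to follow-up or at least 24 months from first dose.
- **End of study:** align the three wordings (synopsis; Protocol 3.3; Appendix 16, 1.1.5 with SAP 4.1) so that the study does not close before that follow-up is complete.
- **SAP 4.1:** replace the 30-day follow-up sentence with the survival schedule in Table 1-1.
- **SAP 4.3.2 item 4:** take death and last-known-alive dates from both the Primary Treatment Phase and Maintenance Phase databases, and report OS24 as not estimable where follow-up does not reach month 24.
- **SAP 3.4 and 1.2.5.1:** reconcile them on whether OS is analysed in Part 2.

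The cost is wording plus calls that the trial already makes. The final OS table and study close come later. OS24 stays imprecise even with full follow-up: 4 of 16 alive gives an exact 95% CI of 7–52%.

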2. STUDY OBJECTIVES AND ENDPOINTS

2.1. Objectives

2.1.1. Primary Objective

To provide continued access to selinexor (KPT-330) for the patients remaining on treatment at the time of the termination of the Primary Treatment Phase.

2.1.2. Secondary Objectives

To collect additional long-term safety, tolerability, and disease response (as collected through standard of care) data for selinexor.

